#### Missing data handling

Three MRIs will be available per patient. TVL will be calculated for each pair of two consecutive MRI scans. Annualized TVL between the baseline (BL) and last follow-up (FU) scan will be calculated by multiplying the TVL between the two consecutive scans and dividing the resulting

TVL with the time interval between BL and FU scan. If for a patient only two MRIs are available, the TVL can still be computed in the same way. If only one MRI is available, TVL cannot be computed, and the patient will be excluded from the study.

As explained above EDSS scores will be measured approximately every 6 months. The annual change of EDSS during the 24 months' time period will be computed by linear regression of EDSS versus time including all visits (see Fig. 3). This approach still works if EDSS measurements are missing. At least two EDSS measurement are needed otherwise the patient needs to be excluded from the study.

#### 5. STUDY LIMITATIONS/STRENGTHS

#### Generalizability of study results

The PENTAGON study if pursued over the full length is able to link results of the phase III clinical trials (RADIANCE and SUNBEAM) regarding the effect of ozanimod on brain volume, and in particular TVL to disability progression in a real world setting. Once confirmed pathological TVL could be considered an independent risk factor for disability worsening. This would then justify inclusion of TVL into the spectrum of treatment targets in MS.

#### Validity of measurement

The PENTAGON study is relatively long due to the involvement of longitudinal brain atrophy parameters: The length is required to warrant that these parameters are measured reliably in single subjects.

#### Bias/confounding and effect modification

A potential difficulty is the influence of different treatment regimens during the study. The treatment can impact TVL, new lesions as well as disability worsening. If the groups 1-3 are unbalanced with respect to different treatments results can be biased. A mitigation can be to use the treatment as a covariate in the statistical analysis.

Patients with recent disease activity are included into the study. There should be no intention to switch from first-line oral immune therapies to other therapy regimens when enrolling the patient into the study. Nevertheless, some patients might switch from first-line oral immune therapies to a second line therapy. For these patients the phenomenon of pseudo-atrophy might occur as it was described in several studies (generally assumed to be due to the resolution of inflammatory edema). Measures TVL needs to be interpreted with caution for these patients. MRI data needed to be excluded if the therapy switch happened less than 6 months before the MRI.

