## Length of follow-up.

The prospective observational study runs for 24 months plus the additional 9 months enrollment period. In total a baseline visit (V1) and two follow-up visits (V2 and V3) per study subject are planned. The main purpose of these visits is to prescribe and schedule a brain MRI examination with the affiliated radiology center. It is important that brain MRIs are performed annually with a minimum of 11 months apart. If the decision is made to extend the study for another 12 months the individual study subject will be followed for 36 months adding another visit (V4) to the study schedule.

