## **Inclusion Criteria**

- MS, as diagnosed by the revised 2017 McDonald criteria
- Exhibiting a relapsing clinical course and history of brain MRI lesions consistent with MS
- Ages 18 to 55 years, inclusive
- Meet one of the following disease activity criteria
  - a. more than 10 T2 lesions at the time of the first visit OR
  - b. at least one documented relapse with the last 12 months prior to the first visit OR
  - c. documented evidence of at least 1 Gd-enhancing lesion on brain MRI within the last 12 months prior to the first visit OR
  - d. documented evidence of at least one new or one enlarging T2 lesion within the last 12 months prior to the first visit.

- Either receive or about to receive first-line oral immune therapies, such as teriflunomide, ozanimod, dimethylfumarate, ponesimod, and diroximethylfumarate.
- No intention to evaluate the patient to switch from first-line oral immune therapies to other therapy regimens.

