# Primary objective: To demonstrate that the change of MS-related disability during a period of 24 months is inversely associated with change of thalamus volume during the same period.

In a previous project sponsored by Celgene, the investigators in this study developed and validated a technique that allows reliable and robust calculation of change in regional volumes based on a longitudinal approach in high-resolution T1w MRIs (Opfer et al. 2020). Such an approach allows percentage estimation of volume change of corresponding regions in successive high-resolution T1w MRIs and is much less susceptible to noise than conventional methods based on calculation of absolute volumes at different time points and a regression model to estimate volume change. It has the potential to overcome the technological limitations that hindered the work of Eshaghi et al. (2018).

[figure not shown]

Figure 3. Linear regression of all EDSS measurements

With this approach, it is methodologically feasible to assess TVL and deep GMVL for individual MS patients.

MS-related disability will be characterized by the Expanded Disability Status Scale (EDSS). The EDSS will be determined at inclusion (baseline), at 24 months after inclusion, and at additional visits at time intervals approx. every 6 months in between. The annual change of EDSS during the 24 months' period will be computed by linear regression of EDSS versus time including all visits (Fig. 3). The slope of the regression line will be the annual change of EDSS.

[figure not shown]
For the correlation analysis annual change of EDSS and annualized TVL will be considered as continuous variables. For all study subjects three high-resolution T1w-MRI scans will available. TVL will be calculated for each pair of two consecutive MRI scans. Annualized TVL between the baseline (BL) and last follow-up (FU) scan will be calculated by multiplying the TVL between the two consecutive scans and dividing the resulting TVL with the time interval between BL and FU scan.

A Pearson correlation analysis will be used to test for with a significance level of p = 0.05. Outcomes can be modelled both as dichotomous (CDP – yes, no) and continuous (raw EDSS score) variables. In case of dichotomous variables, a logistic regression will be used.

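### The pseudo-atrophy exclusion acts on single scans, but TVL is a baseline-to-last-scan interval, so most therapy switches can stay inside the interval analysed

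*Protocol*

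**What the plan says.** Section 5 of the protocol (Bias/confounding and effect modification) expects some therapy changes: "Nevertheless, some patients might switch from first-line oral immune therapies to a second line therapy". It warns that pseudo-atrophy may follow in these patients, an effect "generally assumed to be due to the resolution of inflammatory edema", and asks for caution with their TVL. The operative instruction is: "MRI data needed to be excluded if the therapy switch happened less than 6 months before the MRI".

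The endpoint is defined elsewhere. Section 4 (Primary objective) states: "Annualized TVL between the baseline (BL) and last follow-up (FU) scan will be calculated by multiplying the TVL between the two consecutive scans", and then divides by the time from baseline to that last scan. Missing data handling adds: "If for a patient only two MRIs are available, the TVL can still be computed in the same way". On timing, Length of follow-up says: "It is important that brain MRIs are performed annually with a minimum of 11 months apart". The EDSS side of the correlation is a regression slope over all visits in the 24 months, with no cut at a therapy change. The primary endpoint is a plain Pearson coefficient. Treatment as a covariate is mentioned only as a possible mitigation.

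**The concern.** Volume lost through resolving edema is lost between a scan before the switch and a scan after it. A later second scan does not restore it, so every interval that spans the switch carries the loss. A rule that removes a scan taken soon after the switch, and then lets TVL run from baseline to whichever scan remains, need not remove the artefact.

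If the patients who switch are also those whose EDSS rises faster, artefactual TVL and EDSS slope become linked even when true thalamic loss is unrelated to disability. The planned correlation is only 0.15, so a modest artefact would matter. The protocol intends to use a positive result to support TVL as an independent risk factor and a treatment target.

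**Working it through.** **1. The plan's own figure.** Section 4 (Power/Sample Size) gives r = 0.15, type I error 0.05, type II error 0.20 and N = 347. By Fisher's z, two-sided: n = ((1.960 + 0.842)/atanh(0.15))² + 3 = 346.6, so 347. The figure is reproduced, and N = 347 is used in step 4.

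**2. The rule applied to scans at 0, 12 and 24 months.**

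| Switch (months) | Scan dropped | TVL interval left | Spans the switch? |
|---|---|---|---|
| 0–6 | none | 0–24 | yes |
| 6–12 | month 12 | 0–24 | yes |
| 12–18 | none | 0–24 | yes |
| 18–24 | month 24 | 0–12 | no |

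The rule succeeds in the last row only. In the second row it discards a scan and gains nothing.

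**3. Share of switchers affected.** The protocol gives no switch times, so these are assumptions:
- uniform over 0–24 months: 18/24 = 75%
- uniform, with scans at 11–15 and 23–27 months: 79% (simulation)
- half in the 3 months after the month-12 scan, the rest uniform: 0.5 + 0.5 × 0.75 = 88%
- density falling linearly to zero at month 24: 1 − (6/24)² = 94%
- uniform over 6–24: 12/18 = 67%
- density rising linearly from zero: (18/24)² = 56%
- all in months 12–24: 6/12 = 50%

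These are scenarios, not bounds. Switches concentrated in the last 6 months would give a lower share.

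**4. Induced correlation when the true correlation is zero.** Let f be the share of patients who switch, p = 0.75f the share with a contaminated interval, dE the shift in EDSS slope among switchers and dT the artefactual extra loss (both in SD units). Then, with volume change on one axis,

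r = −p(1 − f)·dE·dT / √{[1 + f(1 − f)dE²]·[1 + p(1 − p)dT²]}.

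None of f, dE or dT is in the protocol.
- Middle case, f = 0.20, dE = dT = 0.5: p = 0.15; r = −0.030/√(1.040 × 1.032) = −0.029. Two-sided test size at N = 347 is 0.084 instead of 0.05.
- f = 0.30, dE = 0.8, dT = 1: p = 0.225; r = −0.126/√(1.134 × 1.174) = −0.109, test size 0.53.
- f = 0.30, dE = dT = 1: r = −0.1575/√(1.210 × 1.174) = −0.132.
- dE = 0: r = 0, no bias.
- dE = −0.3 (switchers do better), f from 5% to 30%, dT from 0.25 to 1: r from +0.003 to +0.043, against the hypothesis.

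**5. An interval-based rule on the same schedule.** Use only scan pairs with no switch inside and whose first scan is not within 6 months after a switch. A switch at 0–6 leaves months 12–24; a switch at 12–24 leaves months 0–12; a switch at 6–12 leaves nothing. Under uniform timing no switcher keeps a contaminated interval, 75% keep a clean 12-month one and 6/24 = 25% lose TVL. With 20% switchers, 0.20 × 0.25 = 5% of patients lose TVL:
- from the 433 expected at month 24: 433 × 0.95 ≈ 411, power 86% at r = 0.15
- from the protocol's minimum of 358: 358 × 0.95 ≈ 340, power 79%

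**The case against.** The strongest reply is that size and direction are not in the document. The protocol does not say how often patients switch, when, why, how large the artefact is, or how EDSS runs in those who switch. Patients enter with "No intention to evaluate the patient to switch from first-line oral immune therapies to other therapy regimens", so a 30% switching rate is a high assumption. That stands. A reader might infer that the primary correlation is biased toward the hypothesis; the documents support only that it may be, if switchers worsen more.

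Three other stronger readings also go too far. A reader might infer that the rule always drops the wrong scan; for a switch in the last 6 months it works. A reader might extend the point to patients who start oral therapy at V1, since the inclusion criteria admit those who "Either receive or about to receive first-line oral immune therapies"; but the protocol ties pseudo-atrophy to a change to second-line therapy and says nothing of it in starters. And a reader might infer that S1 is biased toward an association. The protocol does not call pseudo-atrophy specific to the thalamus; if it also raises whole-brain loss, some affected patients leave the normal-whole-brain subgroup that S1 tests, and the net effect is unknown.

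It can also be said that the protocol already urges caution, records therapy at visits, plans to monitor switching, and may leave interval handling to an analysis plan. That does not answer the point: the exclusion rule and the interval are both fixed here and, followed as written, do not achieve their purpose. Nor does a generous reading of the rule. If it excluded the patient's whole TVL, switches at 0–6 and 12–18 months would still not trigger it: 12/24 = 50% under uniform timing.

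**Conclusion.** The point holds in a limited form. The mismatch between a scan-based exclusion and an interval-based endpoint follows from the protocol's text alone, given annual scans and pseudo-atrophy acting as a step between scans before and after the switch. The share of switchers affected (75%, or about 50% to 94% across the timings tried) depends on assumed switch and scan times.

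The effect on the primary result is conditional: little in the middle case, comparable to the planned effect only when switching is common, the artefact large and switchers clearly worse. It should be corrected before analysis, but it does not show that the primary result will be wrong.

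**What to change.** Replace the scan-based rule with an interval-based one. Exclude from TVL any scan pair whose interval contains a switch to second-line therapy, and any pair whose first scan is less than 6 months after such a switch. Report the correlation under this rule and with all scans, and state in advance which is primary and which is the sensitivity analysis. The Pearson endpoint can stay as it is.

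The data needed are already planned: therapy is recorded at visits and TVL from two scans is already accepted. There are three costs.
- **Patients lost.** About 5% lose TVL at 20% switchers. 411 stays above the 347 needed for the primary endpoint and the 392 listed for S1. 340 falls just below 347; the minimum of 358 is itself already below 392.
- **Noisier intervals.** At 20% switchers about 433 × 0.20 × 0.75 ≈ 65 patients contribute 12 months instead of 24. If their EDSS slope is cut to the same 12 months, three 6-monthly visits replace five. The sum of squared visit times about their mean drops from 2.5 to 0.5, so the slope's error variance is five times as large, assuming independent visit errors. The plan should say whether the EDSS slope is cut in this way.
- **Selective loss.** If switchers truly worsen more, the exclusion removes informative progressors, which is why both analyses should be shown.

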#### 6. STUDY CONDUCT

This study will be conducted in accordance with International Society for Pharmacoepidemiology (ISPE) Guidelines for Good Pharmacoepidemiology Practices (GPP) and applicable regulatory requirements.

#### **Ethics Committee Review and Informed Consent**

#### Ethics Committee Review

The investigator ensures that the required approvals from Ethics Committees, Independent Review Committees, Regulatory Authorities, and/or other local governance bodies are obtained before study initiation at the site.

## **Informed Consent**

In accordance with local regulations, subjects should provide either written or oral consent before enrollment into the study. The participating centers must ensure that patients, or, in those situations where consent cannot be given by patients, their legally acceptable representatives, are clearly and fully informed about the purpose of the study, potential risks, the patient's rights and responsibilities when participating in this study. If local regulations do not require an informed consent document to be signed by the patient, the site staff should document key elements of the informed consent process in the patient's chart.

## Responsibilities within the Study

The study shall be conducted as described in this approved protocol.

#### **Confidentiality of Study Data**

The confidentiality of records that could identify patients within the database must be protected, respecting the privacy and confidentiality rules in accordance with the applicable regulatory requirement(s).

#### **Quality Control**

Quality control measures shall be appropriately applied as defined in the investigator's standard operating procedures (SOPs), which are part of an ISO 9001:2015-certified quality management system (QMS) operated and regularly updated by the investigator and audited by sponsors.

#### **Database Retention and Archiving of Study Documents**

The investigator retains all study records and source documents for the maximum period required by applicable regulations and guidelines, or institution procedures. Location of database and supporting documentation will be outlined in the final observational study report.

## Registration of Study on Public Website

This study will be registered on Deutsches Register Klinischer Studien (https://www.drks.de/drks\_web/).

#### 7. ADVERSE EVENT REPORTING

Not applicable

#### 8. GLOSSARY OF TERMS AND LIST OF ABBREVIATIONS

#### **List of Abbreviations**

| Term         | Definition  |
|--------------|---|
| Investigator | Conducts and sponsors the study and is the warrantor of the study's integrity |
| Participant  | Patient participating in the study  |
| Study center | Clinical site participating in the study                                      |

## 9. SCIENTIFIC PUBLICATIONS

An active participation in scientific and clinical conferences is planned.

An early paper on the results of the secondary data analysis shall be published reporting on the identification of predictive factors for TVL.

